5.1.1.1.2 Study Treatments

The following linaclotide (LIN) treatment groups are defined for this study:

Table 5-2 Treatment Groups by Indication and Treatment Period

	Indication	
Treatment Period	IBS-C	CIC
Open-label	LIN 290 μg	LIN 145 μg
Double-blind	LIN 290 μg	
	LIN 145 μg	LIN 145 μg
	LIN 72 μg	LIN 72 μg
Dose-reduced Open-label	LIN 72 μg	LIN 72 μg

5.1.1.1.3 Statistical Methodology

The methodologies defined below apply as specified to individual endpoints defined in this SAP. When indicated, 95% 2-sided confidence intervals (CIs) and 2-sided p-values will be presented unless otherwise specified.

Table 5–3 Statistical Methodology

Methodology	Description	
Categorical counts	Number of participants in individual categories	
	\circ Participants with ≥ 1 qualifying event counted once per individual category	
Categorical	 Number and percentage of participants in individual categories 	
descriptives	\circ Participants with ≥ 1 qualifying event counted once per individual category	
	• (Optional if specified) N1 if percentage denominator ≠ number of participants in the	
	population (standard percentage denominator)	
	 N1 = participants with non-missing baseline value 	
	_	

Methodology	Description
	 Unevaluable assessments considered missing
	 If specified, participants with baseline PCS values will be excluded
	_
Continuous	• N1, mean, SD, median, minimum, maximum
descriptives	• N1 = participants with non-missing value
CFB descriptives	• Continuous descriptives for baseline, postbaseline, and change from baseline (CFB)
	values
	 N1 = participants with non-missing values at both baseline and the specified
	postbaseline analysis visit
CFB ANCOVA	 Continuous descriptives and SE for baseline, postbaseline, and CFB values
	 Estimates derived from ANCOVA model for CFB value controlling for fixed factors
	(treatment group) and fixed covariates (baseline value)
	Least squares (LS) means and standard errors
	LS mean differences, standard errors, and CIs vs highest LIN dose ¹ Description of the LIN dose of
	 P-values from contrast t-test comparing lower LIN doses² vs highest LIN dose¹
	• N1 = participants with non-missing values at both baseline and the specified
Responder	postbaseline analysis visit
Responder	 Categorical descriptives for responders and nonresponders Nonresponders include:
	Participants who do not meet responder criteria
	 Participants with no postbaseline values
	Risk differences and Wald CIs vs highest LIN dose ¹
	• Unadjusted risk ratios (RRs), odds ratios (ORs), and CIs vs highest LIN dose ¹
	• P-values from Fisher's exact test comparing lower LIN doses ² vs highest LIN dose ¹
Immunogenicity	Categorical descriptives for responders and nonresponders
responder	Nonresponders include:
1	Participants who do not meet responder criteria
	 Participants with no postbaseline values
	Responder rate 1-sided 95% Clopper-Pearson CIs
	• N1 = all participants unless otherwise specified
Time-to-event	Categorical descriptives for participants with events and censoring
	 Censoring includes:
	 Participants who do not meet event criteria
	 Participants with no postbaseline values
	• Quartiles and CIs derived from Kaplan-Meier (KM) nonparametric model using log-
	log transformation of survivor function
	 Estimates derived from Cox proportional hazards model controlling for factor
	(treatment group)
	o Hazard ratios (HRs) and CIs vs highest LIN dose ¹
	• Estimates derived from log-rank model controlling for factor (treatment group)
	o P-values comparing lower LIN doses ² vs highest LIN dose ¹
173.4.C	N1 = all participants unless otherwise specified
KM figure	• Step-function figure of cumulative distribution function (1 – survivor function)
	estimates with censoring indicators, derived from KM nonparametric model

CFB = change from baseline; ANCOVA = analysis of covariance; TTE = time-to-event.

Methodology Description

Raw and derived data listings will be provided, and will be fully defined in the table, figure, and data listing specification document.

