This will be a multicenter, open-label, long-term clinical study to assess the immunogenicity and long-term safety of linaclotide administered orally to adult patients with IBS-C or CIC, and to evaluate lower doses of linaclotide in patients who consider study withdrawal due to intolerable AEs that may be related to the use of linaclotide. Approximately 800 IBS-C or CIC patients (a minimum of 300 each) will be enrolled.

The study will consist of up to a 3-week Screening Period, followed by a 52-week Treatment Period (Figure 9.1–1). Patients who meet the entry criteria will receive once daily, open-label doses of 290 ug linaclotide for patients with IBS-C; those with CIC will receive once daily, open-label doses of 145 ug linaclotide.

In order to limit patient withdrawals from the study due to AEs and to gain information about the effect of lowering the dose in patients who experience intolerable AEs (defined as AEs that subjectively would cause a patient to consider study withdrawal), in particular diarrhea and other GI AEs that may be related to the use of linaclotide, the following intervention (Figure 9.1–2) will be offered as an optional treatment course to such patients, unless deemed clinically inappropriate by the Investigator:

1. A temporary suspension of dosing of up to 7 days. If the dose suspension needs to last longer than 7 days because the intolerable AE has not resolved, then the Investigator should contact the Study Physician to discuss the duration of the dose suspension or withdrawal of the patient from the study. All AEs resulting in the temporary suspension will be recorded on the eCRF.
2. After the intolerable AE has resolved, the patient will be randomized into a Double-blind Treatment Period via an interactive Web response system (IWRS) and will receive dose regimens specific to each indication as follows. If the randomized dose regimen is tolerated, the patient will remain on this dose for the duration of the study (total duration of linaclotide exposure [whether open-label or double-blind] is not to exceed 52 weeks).

IBS-C patients will be randomized in a 1:1:1 ratio to 1 of the following regimens:

- Linaclotide 290 ug every day
- Linaclotide 145 ug every day
- Linaclotide 72 ug every day

[figure not shown]
CIC patients will be randomized in a 1:1 ratio to 1 of the following regimens:

- Linaclotide 145 ug every day
 - Linaclotide 72 ug every day

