9.7.5 Efficacy Analyses

The efficacy analyses will be based on the ITT Population. As this is an open-label study, no inferential statistics will be performed on these endpoints.

Descriptive statistics (n, mean, standard deviation, median, minimum, and maximum) will be presented for continuous variables, and frequency distributions will be presented for categorical variables. These summaries will be presented by indication (IBS-C and CIC) and, where the endpoint is measured for both IBS-C and CIC, pooled across both indications at each scheduled visit the parameter is assessed.

The following parameters will be summarized:

- Constipation severity
- IBS symptom severity (IBS-C only)
- Degree of relief of IBS symptoms (IBS-C only)
- IBS treatment satisfaction (IBS-C only)
- Constipation treatment satisfaction (CIC only)

For recurrence of diarrhea parameters, tables based on the Double-blind ITT Population will specifically refer to recurrence of diarrhea. Listings based on the Randomized Population will identify the patient-specific AEs.

Parameter	Description
[REDACTED]	[REDACTED]
Recurrence of (intolerable) diarrhea	Frequency summary; Fisher exact test, comparing treatment groups.
Time to first recurrence of (intolerable) diarrhea	Parameter = First recurrence of (intolerable) diarrhea date – first randomized dose date + 1; censored at date of last randomized dose for patients who do not have recurrence of (intolerable) diarrhea. Summary statistics for patients who have recurrence of (intolerable) diarrhea; Kaplan-Meier summary statistics, log-rank test, and figure, and hazard ratio per Cox proportional hazards regression model, for all patients, comparing treatment groups, controlling for geographic region.
[REDACTED]	[REDACTED]

[REDACTED]

9.7.8.2.1 *Immunogenicity Assessments*

A patient’s baseline ADA status (ADA positive, ADA negative, or ADA undetermined) will be the assay result of the Treatment Period Day 1 (Visit 2) sample. A patient’s overall postbaseline ADA status will be derived from all postbaseline samples during the Treatment Period and within **7 days** after the last dose of investigational product. The possible categories, dependent on baseline ADA status, are described in [Table 9.7.8.2.1–1](#).

Table 9.7.8.2.1–1. Patient Postbaseline ADA Categorization

Baseline ADA Negative and ADA Undetermined Patients	Baseline ADA Positive Patients
Treatment-induced ADA positive	Treatment-boosted ADA positive

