9.7.9 Determination of Sample Size

The objective of this study is to assess the long-term safety of linaclotide administered to patients with IBS-C or CIC and to determine the potential of linaclotide to induce ADAs. If 0 of 800 patients develop ADAs, the 1-sided 95% upper confidence interval for this rate (0/800 [0%]) is 0.374%.

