4.2 Study Objectives and Endpoints

Each study objective is presented with corresponding endpoint(s) below:

Table 4–1 Study Objectives

Objectives	Endpoints		
Primary			
To assess the potential of linaclotide treatment to induce the development of anti-drug antibodies (ADAs)	Treatment-related ADA positive responder		
Secondary			
To provide additional evidence supporting the long- term safety of linaclotide in adult IBS-C and CIC participants	 Adverse Events Clinical Laboratory Assessments Vital Signs Electrocardiograms Immunogenicity 		
To provide additional evidence supporting the long- term efficacy of linaclotide in adult IBS-C and CIC participants	 Patient assessment of constipation severity Patient assessment of IBS symptom severity (IBS-C only) Degree of relief of IBS symptoms (IBS-C only) IBS treatment satisfaction assessment (IBS-C only) Constipation treatment satisfaction assessment (CIC only) 		
To evaluate lower doses of linaclotide in participants who consider study withdrawal due to intolerable AEs	 Recurrence of diarrhea Recurrence of intolerable diarrhea Time to first recurrence of diarrhea Time to first recurrence of intolerable diarrhea 		

5. Statistical Methodology and Study Endpoints

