5.1.1.1.4 Missing Data

General missing data handling conventions are specified for methodologies in Section 5.1.1.1.3 and summarized as follows:

Table 5–4 Missing Data Handling by Endpoint Type

Parameter type	Timing	Missing Data Handling
Responder	Double-blind Treatment Period	 All participants included unless otherwise specified Participants with no postbaseline values = nonresponders
Immunogenicity responder	Treatment Period	Participants with no postbaseline assessable values excluded
Time-to-event	Double-blind Treatment Period	 Participants not reporting specified event (intolerable diarrhea) during the Open-label Treatment Period excluded Participants with no postbaseline values = censored
CFB ANCOVA	Treatment Period	 If missing covariates (including baseline if applicable) Participant excluded If missing derived value at the specified postbaseline analysis visit: Participant excluded

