5.1.1.3.3 Double-blind Treatment Period Analyses

A set of exploratory analyses will be conducted for Double-blind Safety Population participants, unless otherwise specified, for the subset of participants who experience an intolerable AE during the initial Open-label Treatment Period. Data from the Dose-reduced Open-label Treatment Period following discontinuation of double-blind treatment will be excluded from these analyses.

Pre-randomization (Double-blind Treatment Period baseline) values for efficacy endpoints are defined as the latest available assessment during the Treatment Period on or before the Double-blind start date.

[figure not shown]

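### SAP Table 5-3 uses Wald intervals for responder risk differences although no randomized arm size is planned; a score interval would hold its coverage if the arms turn out small (minor)

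*SAP*

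**What the plan says.** The Responder row of Table 5-3 (SAP 5.1.1.1.3) asks for "Risk differences and Wald CIs vs highest LIN" dose, together with unadjusted risk ratios and odds ratios, and p-values from Fisher's "exact test comparing lower LIN doses" with the highest. Intervals are two-sided 95% unless otherwise stated. Table 5-4 (SAP 5.1.1.1.4) times Responder endpoints to the Double-blind Treatment Period and sets "Participants with no postbaseline values = nonresponders".

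The secondary objective served is "To evaluate lower doses of linaclotide in participants who consider study withdrawal due to intolerable AEs" (SAP 4.2, Table 4-1), whose endpoints include recurrence of diarrhea and of intolerable diarrhea. For recurrence, the parameter table in the protocol's statistical section plans "Frequency summary; Fisher exact test, comparing treatment groups". SAP 5.1.1.3.3 introduces the double-blind work as follows: "A set of exploratory analyses will be conducted for Double-blind Safety Population participants". The table that would tie each endpoint to a method there is not shown.

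The only sample-size statement concerns antibodies: "If 0 of 800 patients develop ADAs, the 1-sided 95% upper confidence interval for this rate" is 0.374% (Protocol 9.7.9, repeated in SAP 5.1.2). Neither document gives a number to be randomized.

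**The concern.** The double-blind dose comparison is the only randomized comparison in the trial. Its size is left to chance. A patient enters after an intolerable event, "defined as AEs that subjectively would cause a patient to consider study withdrawal" (Protocol 9.1). The course is optional, and those who take it are split 1:1:1 in IBS-C or 1:1 in CIC.

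A Wald interval for a difference of two proportions relies on a normal approximation, with each variance estimated from the observed proportion. With few patients and proportions away from one half, it is often too narrow. When each arm has either no events or only events, its width is zero. It can also exclude zero beside a clearly non-significant Fisher p-value. Fisher's test gives no effect size, so the interval is where a reader would look for the dose effect on this scale.

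**Working it through.** **The plan's own figure.** The one-sided 95% Clopper-Pearson upper limit for 0 of 800 is 1 − 0.05^(1/800) = 0.3738%, which matches the stated 0.374%. It says nothing about randomized arms.

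**Possible arm sizes.** About 800 are enrolled with at least 300 per indication (Protocol 9.1), hence 300 to 500 in each. Arm size = enrolled × share randomized ÷ number of arms. The shares are assumed proxies taken from the protocol, not planned numbers.

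| Proxy for share randomized | IBS-C, 3 arms | CIC, 2 arms |
|---|---|---|
| 5%, discontinuation for diarrhea (9.4.4) | 5.0–8.3 | 7.5–12.5 |
| 20% IBS-C, 16% CIC, any diarrhea in pivotal studies (9.4.4) | 20–33 | 24–40 |
| 30%, any diarrhea in long-term studies (7.4) | 30–50 | 45–75 |

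**Formula.** With observed proportions a and b and n per arm, the Wald interval is a − b ± 1.96 × √[a(1−a)/n + b(1−b)/n]. It was compared with the Newcombe interval (built from two Wilson score intervals) and the Miettinen-Nurminen score interval (constrained maximum likelihood variance with factor N/(N−1)).

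**Exact coverage.** Every outcome of two equal binomial arms was enumerated for n = 5, 7, 8, 10, 12, 15, 20, 24, 33, 40 and 50. The documents give no recurrence rate, so two sets were assumed: low (10/30, 5/20, 10/40, 20/40%) and higher (30/50, 40/60, 30/60, 20/60%). That makes 11 × 8 = 88 cells.

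| Per arm, rate set | Wald | Newcombe | Miettinen-Nurminen |
|---|---|---|---|
| 7, low | 76.7–89.8% | 93.7–98.7% | 96.1–98.7% |
| 7, higher | 88.7–92.2% | 91.9–95.9% | 95.6–96.6% |
| 20, all eight pairs | 91.3–94.3% | 94.4–96.3% | 93.5–95.8% |
| 50, all eight pairs | 94.2–94.5% | 94.8–95.9% | 94.5–95.4% |

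| Cells with coverage below 93% | Wald | Newcombe | Miettinen-Nurminen |
|---|---|---|---|
| 5–12 per arm (40 cells) | 32 | 3 | 0 |
| 15–24 per arm (24 cells) | 11 | 0 | 0 |
| 33–50 per arm (24 cells) | 0 | 0 | 0 |
| Worst of all 88 cells | 69.4% | 91.8% | 93.2% |

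The 32 Wald cells divide by arm size as 8 of 8 (n = 5), 8 (n = 7), 6 (n = 8), 6 (n = 10) and 4 (n = 12). Wald never covers more than Newcombe. It covers more than Miettinen-Nurminen once (20 per arm, 30/60%: 94.3 against 93.5%). With equal true rates of 10 to 50%, Wald at 7 per arm covers 92.5 to 97.5%, so it is not poor everywhere.

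**Zero width.** This happens when each arm has no events or only events. At 7 per arm and 5/20% the probability is (0.95^7 + 0.05^7) × (0.80^7 + 0.20^7) = 0.698 × 0.210 = 14.6%. Over the low pairs it is 0.6 to 14.6%, over the higher pairs 0.1 to 0.6%, and at 20 per arm at most 0.4%.

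**Example, 0/7 against 3/7.** The difference is −42.9 points and the standard error is √(0.4286 × 0.5714 / 7) = 0.187. Wald therefore gives −79.5 to −6.2 points, which excludes zero, beside Fisher p = 2 × 35/364 = 0.19. Newcombe gives −75.0 to +1.7 and Miettinen-Nurminen −75.8 to +2.4.

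**Conflict with Fisher.** Probability that the interval excludes zero while Fisher p > 0.05 (Wald, Newcombe, Miettinen-Nurminen):

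- 12 per arm, 10/30%: 23.2, 10.3, 10.3%
- 12 per arm, 30/60%: 15.5, 14.7, 14.7%
- 20 per arm, 30/60%: 22.5, 11.6, 11.6%

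**The case against.** The case for leaving the plan alone is that this is a preference. Wald is standard and prespecified, the analyses are labelled exploratory, Fisher supplies the p-values, and the visible text attaches no decision to this interval. A zero-width interval would stand beside the counts and a Fisher p of 1, so few readers would be misled. All of that stands, and it sets the grade.

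The marked under-coverage also sits at one end of the assumptions. Arms of about 5 to 12 come only from the 5% proxy, which counts discontinuation for diarrhea alone. The actual trigger is any event that makes a patient consider withdrawal, so that end is nearer a floor than a central case. On the other side, not every diarrhea event is intolerable and the course is optional, so the upper end is not established either. The low recurrence rates are not obviously the natural ones, since these patients have already had an intolerable event and the reference arm returns to the starting dose. At the higher rates the gain is smaller: at 7 per arm and 40/60%, Wald covers 91.5%, Newcombe 91.9% and Miettinen-Nurminen 95.9%.

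Finally, the remedy is partial. Disagreement with Fisher is reduced but not removed, and the risk-ratio and odds-ratio intervals in the same row are left as they are. None of this favors Wald, because the score intervals almost coincide with it when arms are large.

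**Conclusion.** The point holds as an optional improvement. The Wald interval is specified and no randomized arm size is planned. At about 5 to 10 per arm it under-covers for most or all of the assumed unequal rates. At 12 per arm it does so for half of them, with a minimum of 90.4%. From about 20 per arm the shortfall is small, and by 33 it is negligible.

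Three assumptions carry this: that the Responder method is applied to diarrhea recurrence, which is inferred from Tables 4-1 and 5-4 and the protocol's Fisher analysis; that the protocol's diarrhea rates bracket the share randomized; and that recurrence rates lie in the ranges shown. The primary antibody analysis uses Clopper-Pearson limits and is not affected.

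**What to change.** In the Responder row of Table 5-3, replace the Wald interval for the risk difference with a Miettinen-Nurminen score interval, which has the better worst case (93.2%), or with Newcombe's (91.8%). Add a note that the interval need not agree with the Fisher p-value.

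The cost is one interval name and one analysis option. Design, data collection and primary analysis do not change. Intervals become wider at low rates and narrower at higher ones. Mean widths in percentage points:

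| Per arm, rates | Wald | Newcombe | Miettinen-Nurminen |
|---|---|---|---|
| 7, 5/20% | 56.7 | 75.6 | 80.1 |
| 7, 10/30% | 72.4 | 77.3 | 82.8 |
| 7, 40/60% | 94.5 | 80.4 | 89.6 |
| 20, 10/30% | 46.4 | 47.6 | 48.6 |

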2.0 SYNOPSIS AND SCHEDULE OF EVALUATIONS

[figure not shown]
CLINICAL STUDY SYNOPSIS: Study LIN-MD-10	
Study Number	LIN-MD-10
Title of Study	An Open-label, Long-term Study to Assess the Immunogenicity of Linaclotide Administered Orally to Adult Patients With Irritable Bowel Syndrome With Constipation or Chronic Idiopathic Constipation
Study Centers (Country)	Approximately 80 (United States)
Development Phase	4
Objectives	The primary objective of this study is to assess the potential of linaclotide treatment to induce the development of anti-drug antibodies (ADAs). The secondary objectives are to provide additional evidence supporting the long-term safety and efficacy of linaclotide in adult irritable bowel syndrome with constipation (IBS-C) and chronic idiopathic constipation (CIC) patients and to evaluate lower doses of linaclotide in patients who consider study withdrawal due to intolerable adverse events (AEs).
Methodology	Multicenter, open-label study. Patients who experience intolerable AEs (defined as AEs that subjectively would cause a patient to consider study withdrawal), may have their dosing suspended and, following resolution of the intolerable AEs, be randomized to receive the same or lower doses of double-blind linaclotide as an optional treatment course. Patients who experience further intolerable AEs after the randomization can be transitioned to open-label 72 ug linaclotide.
Number of Patients	1000 (projected number screened); 800 IBS-C or CIC enrolled. For each patient group (IBS-C or CIC), at least 300 patients are expected to be enrolled.
Diagnosis and Main Criteria for Inclusion	Male and female adult (≥ 18 years of age) outpatients who meet the Rome III criteria for IBS-C or CIC
Test Product, Dosage, and Mode of Administration	Patients with CIC: linaclotide 145-ug capsules, orally, once daily Patients with IBS-C: linaclotide 290-ug capsules, orally, once daily Patients with intolerable AEs will be randomized to receive 290 ug, 145 ug, or the lower (unapproved) dose of 72 ug linaclotide oral capsules for IBS-C; and 145 ug or 72 ug for CIC. Patients who experience further intolerable AEs after the randomization can be transitioned to open-label 72 ug linaclotide.
Duration of Treatment	Up to a 3-week Screening Period, followed by a 52-week Treatment Period
Reference Therapy, Dosage, and Mode of Administration	None
Criteria for Evaluation	Patient-reported assessments
Pharmacokinetic Analysis	Immunogenicity assessments

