5.1 Statistical Methods Planned in the Protocol and Determination of Sample Size

This statistical analysis plan (SAP) expands the statistical section of the protocol and contains a detailed description of methods to analyze data collected in the study. The text portion of the SAP will be included in the CSR report as Appendix 16.1.9.

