5.1.1.3.2	endpoints with baseline values	
5.1.1.3.3	Changed population to DB Safety for selected analyses	Incorrectly specified in protocol
5.1.1.3.3	Changed assignment of values on same date as DB start	Value from DB start date assumed to
	date from post-rand to pre-rand	be before first DB administration
		Clarification
5.1.1.4.6	Revised details of ADA classification rules; Revised	Clarification
	listing specification	
		Correction

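### Does the SAP need correcting because its time-to-recurrence models leave out the geographic region term named in the protocol?

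*SAP*

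**What the plan says.** The table in Protocol 9.7.5 covers time to first recurrence of (intolerable) diarrhea in patients randomized after an intolerable adverse event. It lists Kaplan-Meier statistics, a log-rank test and a figure, and then a "hazard ratio per Cox proportional hazards regression model, for all patients, comparing treatment groups, controlling for geographic region".

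SAP 5.1.1.1.3, Table 5-3, time-to-event row, gives two model lines. The Cox line reads "Estimates derived from Cox proportional hazards model controlling for factor", with treatment group in brackets as the only factor. The log-rank line reads "Estimates derived from log-rank model controlling for factor (treatment group". Region is in neither.

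SAP 5.1 describes its relation to the protocol: "This statistical analysis plan (SAP) expands the statistical section of the protocol". SAP 5.1.1.3.3 introduces the double-blind comparisons with "A set of exploratory analyses will be conducted for Double-blind Safety Population participants". The History of Change in SAP section 8 has an entry for that section: "Changed population to DB Safety for selected analyses", with the reason that the protocol had it wrong. No entry that can be read mentions region.

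The visible text gives no region categories. The synopsis puts the centers at "Approximately 80 (United States", all in one country. Protocol 9.1 describes the randomization by indication and ratio only, for example "IBS-C patients will be randomized in a 1:1:1 ratio to 1 of the following regimens".

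**The concern.** A SAP that expands the protocol would be expected to carry over a model term that the protocol names, or to say why it does not. Here the term is absent. The same SAP section has a logged and explained departure on the analysis population, so silence on region looks like an oversight.

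Two approved documents then give two models for the randomized evidence on a stated secondary objective, the evaluation of lower doses. One of those models needs a region grouping that the visible text does not define. If the grouping were chosen late, an analyst could pick between two hazard ratios, or two p-values, after seeing both. The randomized arms may be small, so the two could differ noticeably.

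**Working it through.** **1. What the texts require.** In the protocol sentence, region is attached directly to the Cox hazard ratio. Whether it reaches back to the log-rank test is ambiguous. The clear mismatch is therefore in the Cox line; for the log-rank test it is only possible.

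Table 5-3 is a menu of methods. The SAP says its entries apply as specified to individual endpoints. The rows for the double-blind endpoints are not shown: the visible table numbers go from 5-13 to 5-20. A region term or an explanation could stand there, or in SAP section 6, most of which is also not shown.

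**2. The plan's own figure.** No power, event count or hazard ratio is given for this endpoint. The only precision figure concerns the antibody rate: 1 - 0.05^(1/800) = 0.374%. It reproduces and does not depend on the region question.

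**3. Arm size (assumed).** The documents do not say how many patients will be randomized. Two rates in the protocol give a range, with 300 to 500 patients per indication.

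- Low: 5% discontinuing for diarrhea (Protocol 9.4.4). 800 × 0.05 = 40 in all, or 15 to 25 per indication. Dividing by 3 gives 5 to 8 per arm in IBS-C; dividing by 2 gives 7 to 12 per arm in CIC.
- High: about 30% with diarrhea in the long-term studies (Protocol 7.4), all randomized. 800 × 0.30 = 240, or 90 to 150 per indication. That is 30 to 50 per arm in IBS-C and 45 to 75 in CIC.

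The low end is probably too low. It counts actual discontinuations, whereas the trigger here is only considering withdrawal, over 52 weeks.

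**4. Effect of region on the log-rank test.** Assumptions: two arms, four equal regions, exponential times, censoring at 50 weeks, recurrence 70% versus 30%, no true region effect, 4,000 trials per setting.

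| Per arm | Information lost by stratifying | Power, unstratified | Power, stratified | Opposite sides of p = 0.05 |
|---|---|---|---|---|
| 8 | 23% | 38% | 28% | 19% |
| 12 | 15% | 53% | 44% | 16% |
| 50 | 3% | 99% | 99% | 0.5% |

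With recurrence 50% in both arms, type I error was 5.2% unstratified and 5.1% stratified at 8 per arm, and 5.1% and 5.4% at 12.

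A real region effect (SD 0.5 on the log hazard) gives power of 34% versus 26% at 8 per arm, 50% versus 44% at 12, and 98% for both at 50.

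**5. A weaker effect and intermediate arms.** With a hazard ratio of 0.4, about 50% recurrence in the higher-risk arm, 10 to 30 per arm and 1,500 trials per setting, type I error was 4.5% to 5.7% unstratified and 4.2% to 6.1% stratified. Power differed by at most about 5 points, in either direction. For example, at 30 per arm it was 55.7% versus 53.0% with no region effect, and 52.1% versus 57.4% with a region effect of SD 0.7.

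**6. Reading.** Both tests are valid throughout. Where the choice matters, in very small arms, it is the SAP's simpler model that keeps more power. Where arms are large, the choice hardly matters. These simulations concern the log-rank test; the effect on the Cox hazard ratio was not quantified.

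**The case for a change.** The strongest case for acting is that the remedy is nearly free. One sentence in the SAP would record that region was dropped and why, and would close off a later choice between models. Table 5-3 does name extra terms where it wants them: the ANCOVA row lists the baseline value. The wording about exceptions in the time-to-event row concerns the denominator, not the model. The endpoints appear in SAP Table 4-1 under a secondary objective and will carry p-values, so calling them exploratory does not make them invisible. At 8 per arm the two tests disagreed at p = 0.05 in about one simulated trial in five.

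Much of this stands. The texts differ, and a short note would be good housekeeping. Three parts are weaker.

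- **The silence proves little.** The History of Change records an amendment of the SAP against its own predecessor. If that predecessor already had treatment-only models, no entry was due. Some entries also survive only as a bare reason with no section or description.
- **A missing region definition cannot be asserted.** Most of SAP section 6 is not shown, and the randomization list is a separate file. A note stating that no categories exist would claim something the public text cannot support.
- **The disagreement rate depends on the assumptions.** At 8 per arm it falls to about 10% with two regions, or with recurrence of 50% versus 30%. With four regions and 70% versus 30% it is about 9% to 10% at 20 per arm and 4% at 30.

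**Conclusion.** The protocol and the visible SAP differ on one model term, and no change to the plan follows. The SAP gives the operative specification, and it is sound: randomization makes the treatment-only comparison valid, with type I error near 5% in every null setting tried. The likely remedy would leave that model in place and add a line of record, with an optional sensitivity analysis in an exploratory part of the study. No estimate, test or conclusion in the plan would change, and the primary antibody analysis is not involved.

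In the settings tried, the power difference runs from about 10 points in favor of the SAP's model at 8 per arm (70% versus 30%) to about 5 points the other way at 30 per arm with a strong region effect. At 50 per arm it is under 1 point. This rests on assumed arm sizes, recurrence rates and a four-region grouping. It also assumes that the randomization was not stratified by region, which the visible text does not say. If it was, the unstratified test would be slightly conservative, not invalid.
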